## Appendix 1. Schedule of Assessments and Procedures

	Pre-Screening a	Screening b,f				Treatment Period c				Follow-Up d	ET
		Study Day -28 to -21	Study Day -14 to -7	Study Day -7	Study Day 1 e	Week 2/ Study Day 15 ± 3 days	Week 6/ Study Day 43 ± 3 days	Week 10/ Study Day 71 ± 3 days	Week 12/ Study Day 85 or up to 3 days prior to Study Day 85	Study Day 113	
	Visit Identifier	Visit S1	Visit S2	Visit S3	Visit T1	Visit T2	Visit T3	Visit T4	Visit T5	Visit FU1	
HbA1c	X	X			X				X		X
Cystatin-C, ANGPTL4, adiponectin					X				X		X
hsCRP, SAA, IL-6, and fibrinogen					X				X		X
Lipoprotein size and particle number					X				X		X
Randomization					X						
Study drug administration s					X	X	X	X			
Dispense study drug and instructions					X	X	X	X			
Compliance check					X	X	X	X	X		X
Distribute drug diary					X	X	X	X			
Dietary assessment (self-reported) t	X	X	X	X	X	X	X	X			
12-lead ECG u		X			X	X	X	X	X		X
Initiate wash-out	X										
Adverse events	X v	X v	X	X	X	X	X	X	X	X	X
Concomitant medications	X	X f	X	X	X	X	X	X	X	X	X
Reserve serum samples w					X	X	X	X	X		X
Reserve plasma PK samples x					X	X	X	X	X		X
Collect drug diary						X	X	X	X		X
Reserve genotyping sample					X						

Apo = apolipoprotein; ECG = electrocardiogram; eCRF = electronic case report form; ET = Early Termination; HBV = hepatitis B virus; HbA1c = hemoglobin A1c; HCV = hepatitis C virus; HDL-C = high-density lipoprotein cholesterol; HIV = human immunodeficiency virus; HoFH = homozygous familial hypercholesterolemia; hsCRP = high-sensitivity C-reactive protein; LDL-C = low-density lipoprotein cholesterol; Lp(a) = lipoprotein(a); NCEP ATP-III = National Cholesterol Education Program Adult Treatment Panel III; NGAL = neutrophil gelatinase-associated lipocalin; non-HDL-C = non-high-density lipoprotein cholesterol; TC = total cholesterol; TG = triglyceride;

## Appendix 1. Schedule of Assessments and Procedures

	Pre-Screening a	Screening b,f				Treatment Period c				Follow-Up d	ET
		Study Day -28 to -21	Study Day -14 to -7	Study Day -7	Study Day 1 e	Week 2/ Study Day 15 ± 3 days	Week 6/ Study Day 43 ± 3 days	Week 10/ Study Day 71 ± 3 days	Week 12/ Study Day 85 or up to 3 days prior to Study Day 85		
	Visit Identifier	Visit S1	Visit S2	Visit S3	Visit T1	Visit T2	Visit T3	Visit T4	Visit T5	Visit FU1	

TSH = thyroid-stimulating hormone; VLDL-C = very low-density lipoprotein cholesterol.

- a Only subjects requiring a Wash-Out Period will participate in the Pre-Screening Visit. Specifically, PCSK9 inhibitors will require an 8-week Wash-Out Period, fibrates will require a 6-week Wash-Out Period, and niacins, OMG-3, bile acid sequestrants or other lipid-regulating therapies will require a 4-week Wash-Out Period, prior to the Screening Visit.
- b All eligible subjects will participate in the Screening Visit up to 28 days prior to Study Day 1. For subjects taking the required stable statin therapy for > 12 weeks at the Screening Visit and do not require a Wash-Out Period, the Screening Visit will be their first study visit.
- c Study assessments will be completed ± 3 days of given time point for all study visits from Study Day 1 through Week 10. Week 12 assessments can be performed up to 3 days prior to Study Day 85, but not after Study Day 85.
- d The Follow-up Visit will be conducted as a telephone call 4 weeks (± 3 days) after the last dose of study drug, unless the subject requires a site visit due to an abnormal result at Week 12 (or the ET Visit, if applicable) or an ongoing treatment-related adverse event.
- e Procedures will be performed pre-dose. The Investigator will inquire with the subject at Study Day 1 to determine if there have been any changes in the subject's health affecting eligibility or requiring an update to their medical and surgical history.
- f For subjects who required a Wash-Out Period and completed the Pre-Screening Visit, the following Screening Visit procedures will not be repeated: informed consent, full physical examination, height, TSH, HbA1c, and serology (HBV, HCV, and HIV) screening. Updates, as needed, will be made to medical/surgical history, demographics, and concomitant medications.
- g A full physical examination includes genitourinary examination per the Investigator's discretion and does not include a rectal examination.
- h Only for subjects who required a Wash-Out Period and completed the full physical examination at the Pre-Screening Visit.
- i Only for subjects who had an abnormal result at Week 12 (or the ET Visit, if applicable) or an ongoing treatment-related adverse event.
- j Vital signs include pulse rate, blood pressure, respiration rate, and temperature. Blood pressure should be obtained in the seated position, after the subject has rested comfortably for at least 5 minutes. Blood pressure at the Screening Visit should be obtained in both arms and the arm with the highest value should be used for ongoing monitoring throughout the rest of the study. If an automated assessment is performed, the same machine should be used for the subject throughout the study when possible. Care should be taken to ensure an appropriate cuff size is utilized.
- k Height will be measured only at the subject's first study visit, either at the Pre-Screening Visit or the Screening Visit.
- l Urine will be collected for a full urinalysis at the lab including protein:creatinine ratio and albumin:creatinine ratio at the Prescreening/screening Visit, Study Day 1, Week 6, Week 12, the Follow-up Visit (only for subjects who had an abnormal result at Week 12 [or the ET Visit, if applicable] or an ongoing treatment-related adverse event), and the ET Visit, if applicable. Urinary NGAL will be measured at Study Day 1, Week 6, Week 12, the Follow-up Visit (only for subjects who had an abnormal result at Week 12 [or the ET Visit, if applicable] or an ongoing treatment-related adverse event), and the ET Visit, if applicable.
- m For women of child-bearing potential only, a serum pregnancy test will be conducted at the Screening Visit, Week 12, and the ET Visit, if applicable. A urine pregnancy test will be conducted at the Pre-Screening Visit, Study Day 1, Week 2, Week 6, and Week 10.
- n Clinically significant abnormal creatinine results at Week 12 (or the ET Visit, if applicable) will also be followed-up 2 weeks (± 3 days) after the last dose of study drug in

## Appendix 1. Schedule of Assessments and Procedures

	Pre-Screening a	Screening b,f				Treatment Period c				Follow-Up d	ET
		Study Day -28 to -21	Study Day -14 to -7	Study Day -7	Study Day 1 e	Week 2/ Study Day $15 \pm 3$ days	Week 6/ Study Day $43 \pm 3$ days	Week 10/ Study Day $71 \pm 3$ days	Week 12/ Study Day 85 or up to 3 days prior to Study Day 85	Study Day 113	
	Visit Identifier	Visit S1	Visit S2	Visit S3	Visit T1	Visit T2	Visit T3	Visit T4	Visit T5	Visit FU1	

addition to the 4 week ( $\pm 3$  days) Follow-up Visit. See Appendix B for a list of analytes and description of when repeat or reflexive testing will be required.

- a Thyroid-stimulating hormone, HbA1c, and serology (HBV, HCV, and HIV) will be measured at the subject's first study visit, either at the Pre-Screening Visit, if applicable, or the Screening Visit.
- b Includes non-HDL-C, TC, TG, HDL-C, VLDL-C and HDL-TG. Fasting will be defined as no food or caloric beverage for at least 10 hours prior to sample collection. Subjects will be permitted to have water, black tea or black coffee.
- c Includes TG only. Fasting will be defined as no food or caloric beverage for at least 10 hours prior to sample collection. Subjects will be permitted to have water, black tea or black coffee.
- d Includes ApoB, ApoA-I, ApoA-II, ApoC-II, ApoC-III, and ApoE. Fasting will be defined as no food or caloric beverage for at least 10 hours prior to sample collection. Subjects will be permitted to have water.
- e Study drug will be administered at the site on Study Day 1. Subjects will self-dose at all other times during the Treatment Period.
- f Subjects will self-report compliance to a stable, heart-healthy diet.
- g Subjects should be lying quietly in a fully supine position for at least 10 minutes prior to each 12-lead ECG.
- h Serious adverse events that occur prior to the first dose of study drug (Study Day 1) should be reported as an update to medical history as well as be reported on the appropriate adverse event eCRF.
- i The following may be analyzed: RLP-C, RLP-TG and RLP-apoB, Lp(a), ox-LDL, and Lp-PLA2.
- j Plasma samples collected at Week 2, Week 6, Week 10, Week 12 and ET will be used for the analysis of gemcabene PK. The plasma sample collected at Day 1 will be reserve.

## Appendix 2. Prior and Concomitant Medications Date Imputation

Imputation Rules for Partial Dates (D = day, M = month, Y = year)			
Parameter	Missing	Additional Conditions	Imputation
Start date	D only	M and Y same as M and Y of first dose of study drug	Date of first dose of study drug
		M and/or Y not same as date of first dose of study drug	First day of month
	M and D	Y same as Y of first dose of study drug Y not same as Y of first dose of study drug	Date of first dose of study drug Use Jan 01 of Y
M, D, and Y	None - date completely missing		Day prior to date of first dose of study drug
	D only	M and Y same as M and Y of last dose of study drug	Date of last dose of study drug
		M and/or Y not same as date of last dose of study drug	Last day of month
M and D	Y same as Y of last dose of study drug		Date of last dose of study drug
	Y not same as Y of last dose of study drug		Use Dec 31 of Y
M, D, and Y	None - date completely missing and NOT ongoing		Date of last dose of study drug

Note: In all cases, if an estimated start date is after a complete stop date, use the first day of the stop date month.

Similarly, if the estimated stop date is before a complete or imputed start date, use the last day of the start date month.

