### 6.2.3 Exploratory Endpoints

The exploratory efficacy endpoints are as follows:

- CI [REDACTED]

- CI [REDACTED]
- [REDACTED]

Appendix 3 contains anatomical therapeutic chemical (ATC) categories and descriptions that will be used to identify anti-diabetes pharmacologic therapy for subjects. If an anti-diabetes pharmacologic therapy has a start date on or before first dose of study drug (ie, medication start date less than, or equal to day of first dose of study drug) and a stop date on or after first dose of study drug (ie, medication stop date greater than, or equal to day of first dose of study drug) it will be used in analysis. Partial and missing dates will be imputed using rules in Appendix 2.

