## **8.2 Per-Protocol Set**

The Per Protocol Set (PPS) will be determined partially through sponsor review of blinded individual subject data and partially through objective criteria. Both methods will be completed prior to database lock. The following criteria for FAS subjects should be met in order to qualify for the PPS:

- Subjects completed the 12-week Treatment Period
- Subjects taking a statin in combination with study drug did not experience a change or interruption in statin dose
- Subjects took the same study drug medication for the entire study duration and it matches the treatment to which they were randomized

Additionally, a sponsor review for any other major protocol deviations that may impact efficacy (such as low study medication compliance [i.e., approximately 80% or lower] after Week 6) will be conducted, and further subjects could be excluded from the PPS. The PPS will be used to assess robustness of the analysis results. Subjects excluded from the PPS and the reason for exclusion will be provided in the listings.

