## **13.2 Prior and Concomitant Medications**

Prior and concomitant medications will be coded using the World Health Organization (WHO) Drug Dictionary version 01 Mar 2016. A prior medication is defined as a medication with a stop date prior to the date of the subject's first dose of study drug (ie, medication stop date less than date of first dose of study drug). A concomitant medication is defined as a medication with a start date on or before the date of the subject's last dose of study drug (ie, medication start date less than or equal to date of last dose of study drug) and a stop date on or after the date of the subject's first dose of study drug (ie, medication stop date  $\geq$  date of first dose of study drug);

thus, a medication that is ongoing at the time of the subject's first dose of study drug is considered concomitant. Partial and missing dates will be imputed using rules in [Appendix 2](#).

Prior and concomitant medications will be summarized in separate tables and listings. Medications taken within the period after last dose date and follow-up visit will not be summarized in the tables, but will be included in the concomitant medications listing. Medications will be summarized by ATC level 3 (level 3 indicates the therapeutic/pharmacologic subgroup) alphabetically and preferred name (decreasing frequency in the gemcabene 600mg column, then gemcabene 300 mg column within each ATC) by randomized treatment group for the SAS. At each level of summarization, subjects who report one or more medications within a given level (eg, ATC and preferred name) will only be counted once at that level.

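### In two patterns of incomplete medication dates, the SAP Appendix 2 note moves a recorded pre-treatment stop past first dose, so a prior medication is tabulated as concomitant

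*SAP*

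**What the plan says.** SAP Appendix 2 fills in partial medication dates.

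- **Start wholly missing:** "Day prior to date of first dose of study drug".
- **Start with only the year known:** the first-dose date if the year is the first-dose year, otherwise 1 January of the recorded year.
- **Stop lacking only the day:** under the condition "M and/or Y not same as date of last dose of study drug", the last day of the recorded month.
- **Stop with only the year known:** under the condition "Y not same as Y of last dose of study drug", 31 December of the recorded year.

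A two-sentence note resolves conflicts. If the stop date is complete and the estimated start falls after it, the start moves back to the first day of the stop month. If the stop is itself estimated, the note goes the other way: "if the estimated stop date is before a complete or imputed start date, use the last day of the start date month".

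SAP 13.2 classifies on the resulting dates: "A prior medication is defined as a medication with a stop date prior to the date of the subject's first dose of study drug". A medication is concomitant if it started on or before last dose and stopped on or after first dose. Prior and concomitant medications are tabulated separately by randomized group for the Safety Analysis Set.

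**The concern.** A stop recorded as a month or year that lies wholly before first dose already settles the classification. Whatever the missing day, the drug is prior. The second sentence of the note nevertheless treats a placeholder start as firmer than the recorded stop and moves the stop past first dose. This is not a cautious choice about something unknown, because an assumption displaces recorded information. It also makes the result depend on how precisely the stop was written: 10 March gives prior, while March alone gives concomitant.

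The concomitant-medication table is a natural place to look for lipid-altering drugs taken during treatment. Protocol 4.2 (exclusion 16) and 5.6.2 require fibrates, omega-3 products and niacin to be washed out before screening. A false entry for one of these would suggest on-treatment use that the subject's own record contradicts, and the drug would be absent from the prior-medication table.

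**Working it through.** **Inputs.** The date rules and note are from SAP Appendix 2, and the definitions are from SAP 13.2. The dosing dates are an assumption: first dose F = 15 Jun 2017 and last dose 7 Sep 2017 (Day 85, the end of the treatment period in SAP Table 1). The plan gives no figure on this point to reproduce.

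**Worked records, rules applied literally.**

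| Recorded start | Recorded stop | Imputed start | Imputed stop | After the note | Class |
|---|---|---|---|---|---|
| missing | Mar 2017 | 14 Jun 2017 | 31 Mar 2017 | 14 to 30 Jun 2017 | concomitant |
| missing | 2016 | 14 Jun 2017 | 31 Dec 2016 | 14 to 30 Jun 2017 | concomitant |
| 2017 | Mar 2017 | 15 Jun 2017 | 31 Mar 2017 | 15 to 30 Jun 2017 | concomitant |
| missing | 10 Mar 2017 | 14 Jun 2017 | as recorded | 1 to 10 Mar 2017 | prior |
| 2017 | 10 Mar 2017 | 15 Jun 2017 | as recorded | 1 to 10 Mar 2017 | prior |
| Jan 2017 | Mar 2017 | 1 Jan 2017 | 31 Mar 2017 | unchanged | prior |
| 2016 | Mar 2017 | 1 Jan 2016 | 31 Mar 2017 | unchanged | prior |

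The first two rows are pattern (i) and the third is pattern (ii). The last four show where the rules work.

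**General result.**

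- Pattern (i): the start is F − 1 and the stop becomes the last day of the month containing F − 1. That day is on or after F unless F is the 1st of a month. In that case the stop is F − 1 and the record stays prior.
- Pattern (ii): the start is F and the stop becomes the last day of F's month. That day is never before F, so the record is always concomitant.

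**Counts over all first-dose dates in 2017.**

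- Pattern (i), stop known to a month three months earlier, or only to the previous year: 365 − 12 = 353 of 365 (96.7%) become concomitant.
- Pattern (i), every stop month from 1 to 12 months before first dose: 12 × 365 = 4380 combinations, less 12 × 12 = 144 exceptions, leaves 4236 (96.7%).
- Pattern (ii), stop month three months earlier in the same year: this needs a first dose from April on, so 365 − (31 + 28 + 31) = 275 dates, and 275 of 275 become concomitant.
- Complete stop date: 0 of 365.

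**Size in a table.** One subject in a planned 30-subject arm is 1/30 = 3.3 percentage points. SAP 13.2 counts a subject once per level, so this is the most that one false entry can add to a given row.

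**The case against.** The strongest reply is that this is a rare drafting slip in a descriptive table. Much of that stands.

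- **Incomplete dates alone do not trigger it.** A reader might infer that any record with both dates incomplete is affected. The last two rows of the worked table show otherwise: a start such as Jan 2017 or 2016 with a stop of Mar 2017 stays prior.
- **The rates are conditional.** A reader might take 97% or 100% as the share of medication records affected. They describe what happens once a record has the pattern, and the documents give no count of such records.
- **Few such records may exist.** Protocol 5.6.4 sets recording from informed consent, and SAP Table 1 starts wash-out no earlier than Day -84, which is 23 Mar 2017 for the assumed first dose. A stop in 2016 would normally predate consent. Drugs stopped for wash-out are stopped at the Pre-Screening Visit, where the date should be known, and Protocol 10.1 has missing data queried. This makes the patterns less common but does not exclude them. A six-week fibrate wash-out plus 28 days of screening is 70 days, which reaches back to 6 Apr 2017. A stop recorded only as April, with an unknown start, is pattern (i).
- **The per-protocol set.** A reader might infer that compliant subjects would be dropped. SAP 8.2 provides for "a sponsor review for any other major protocol deviations that may impact efficacy" on blinded individual data, and nothing says that review uses Appendix 2 dates.
- **Anti-diabetes therapy.** SAP 6.2.3 says "Partial and missing dates will be imputed using rules in Appendix 2", and both patterns would pass its test of start on or before and stop on or after first dose. But SAP 4.3 drops the dosage-decrease analysis, and the remaining exploratory endpoints are redacted, so no effect on an analysis can be shown.

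None of this defends the rule. The words 'or imputed' are explicit, and no other provision protects the recorded stop.

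**Conclusion.** The concern holds in narrow form. The second sentence of the Appendix 2 note gives a wrong classification in two patterns: a wholly missing start with a partial stop entirely before first dose (except when first dose is on the 1st of a month), and a start known only as the first-dose year with a stop known only to an earlier month of that year.

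The visible consequence is confined to the prior and concomitant medication tables. It is at most 3.3 percentage points per false entry in a 30-subject column, and only if the subject has no true entry at that level. The total effect is unknown because the number of such records is not given.

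A reader might fear for the efficacy results, and the documents do not support that. The primary triglyceride analysis in SAP 11.1 does not use these dates. The stable-statin definition in SAP 10.2 needs a start at least 12 weeks before the first screening visit, and a placeholder start at or one day before first dose cannot meet it.

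The conclusion rests on a literal reading of the note. The 2017 calendar is only an illustration, since the general result does not depend on the year.

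**What to change.** In the Appendix 2 note, delete 'or imputed' from the second sentence and add:

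> If the start date is completely missing, or only its year is known, and the imputed start is after an imputed stop, keep the imputed stop and set the start to the first day of the stop month (1 January of the stop year if the month is unknown), provided this agrees with any recorded start year. Records whose recorded start and stop components contradict each other are queried. A medication whose recorded stop month or year is entirely before first dose is a prior medication.

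The three misclassified records above then become 1 to 31 Mar 2017, 1 Jan to 31 Dec 2016, and 1 to 31 Mar 2017. All are prior, because the stop stays before first dose. The proviso and the query rule stop the new text from overwriting a recorded start, for example a start of Apr 2017 with a stop of Mar 2017.

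One case needs the present rule kept: a partial start after last dose with a wholly missing stop. With last dose 7 Sep 2017, a start of Oct 2017 gives 1 Oct against an imputed stop of 7 Sep, with no contradiction in the record. A clause should retain the move to the end of the start month there.

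The cost is a few sentences in the SAP and a small change to the date-derivation program, with no new data collected. Only contradictory records would need a site query.

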### Appendix 3. ATC Categories and Descriptions of Anti-diabetes Pharmacologic Therapy

The WHO Drug Dictionary version 01 Mar 2016 was used to identify the following ATC categories and descriptions which will be used to identify anti-diabetes pharmacologic therapy.

ATC3/ATC3 Description 	ATC4/ATC4 Description
A10A/INSULINS AND ANALOGUES	A10AB/Insulins and analogues for injection, fast-acting
A10A/INSULINS AND ANALOGUES	A10AC/Insulins and analogues for injection, intermediate-acting
A10A/INSULINS AND ANALOGUES	A10AD/Insulins and analogues for injection, intermediate- or long-acting combined with fast-acting
A10A/INSULINS AND ANALOGUES	A10AE/Insulins and analogues for injection, long-acting
A10A/INSULINS AND ANALOGUES	A10AF/Insulins and analogues for inhalation
A10B/ BLOOD GLUCOSE LOWERING DRUGS, EXCL. INSULINS	A10BA/Biguanides
A10B/ BLOOD GLUCOSE LOWERING DRUGS, EXCL. INSULINS	A10BB/Sulfonylureas
A10B/ BLOOD GLUCOSE LOWERING DRUGS, EXCL. INSULINS	A10BC/Sulfonamides (heterocyclic)
A10B/ BLOOD GLUCOSE LOWERING DRUGS, EXCL. INSULINS	A10BD/Combinations of oral blood glucose lowering drugs
A10B/ BLOOD GLUCOSE LOWERING DRUGS, EXCL. INSULINS	A10BF/Alpha glucosidase inhibitors
A10B/ BLOOD GLUCOSE LOWERING DRUGS, EXCL. INSULINS	A10BG/Thiazolidinediones
A10B/ BLOOD GLUCOSE LOWERING DRUGS, EXCL. INSULINS	A10BH/Dipeptidyl peptidase 4 (DPP-4) inhibitors
A10B/ BLOOD GLUCOSE LOWERING DRUGS, EXCL. INSULINS	A10BX/Other blood glucose lowering drugs, excl. insulins
A10X/OTHER DRUGS USED IN DIABETES	A10XA/Aldose reductase inhibitors

ATC = anatomical therapeutic chemical, DPP = dipeptidyl peptidase

 All medications listed have ATC1/ATC1 Description = A/ALIMENTARY TRACT AND METABOLISM and ATC2/ATC2 Description = A10/DRUGS USED IN DIABETES.
